9.6 Data Management

9.6.1 Data Processing

Data for this prospective registry will be managed with an electronic data capture (EDC) platform, which is 21 CFR Part 11 compliant. Participants and their HCPs will provide data over the phone or by completing a paper case report form (CRF), which can be submitted to the registry via mail or fax. The data will be reviewed by a registry clinical research associate for correctness and completeness and entered into the database.

9.6.2 Software and Hardware

Power calculations presented in this protocol were conducted using SAS statistical software and a 1-sample binomial distribution with a 1-sided Type I error rate of 5%. Data analyses will be performed similarly using SAS (version 9.2 or higher; SAS Institute, Cary, NC).

9.7 Data Analysis

Registry Case Management and Disposition

Prospective Registry Reports

The registry will encourage prospective registration, which is defined as registration of a pregnancy exposure prior to knowledge or perceived knowledge of the pregnancy outcome (e.g., structural defect or genetic abnormality noted on a prenatal test). Those with no abnormalities identified on a prenatal test prior to enrollment will be considered prospective and included in the analysis. The rationale, potential bias, and analytic techniques to address any bias that may be introduced by this practice are addressed in [Section 9.7.4](#).

Data from HCP provider networks and HMOs that provide de-identified data on all exposed pregnancies in their network will fall into the category of prospective registry reports, as these networks/HMOs provide objective data on every pregnancy exposure in the network/HMO, both positive and negative outcomes. Thus, they avoid the reporting bias inherent in retrospective reporting only after a negative outcome has been noted.

Retrospective Registry Reports

Retrospective reports will also include subjects for whom the pregnancy outcome has already occurred or an abnormality has been identified on a diagnostic or screening prenatal test prior to enrollment. Retrospective reports can be biased toward the reporting of more unusual and severe cases and are less likely to be representative of the general population experience than reports reported prior to knowledge of outcome. Therefore, retrospective reports will not be included in the primary analysis and statistical calculation of risk. Retrospective reports with reported MCMs and/or spontaneous fetal losses will be reviewed to aid in detection of early signals and listed in registry reports. Retrospective reports will not be actively solicited by the registry and will not be captured in the registry database unless a congenital anomaly is reported.

Loss to Follow-Up

For a prospective report or pregnancy where follow-up information on the pregnancy outcome (live birth, fetal loss, etc.) is never obtained or is unavailable, the pregnancy will be considered lost to follow-up. Subjects lost prior to pregnancy outcome will be tallied in the registry reports but not included in the statistical analyses.

Duplicate Registry Reports

With registry reports coming from multiple health care providers, health care provider networks, and HMOs, it is important to ensure that each case is counted only once ([NBDPN, 2004](#)). Identification of duplicate reports may be problematic for the anonymously reported de-identified cases where there is no specific identifying information. Reports received by the registry will be reviewed for possible duplicate reporting. On receipt of a registration form, the report will be compared with other reports made by the same reporter or compared with other data (such as age, LMP, EDD, and exposure information) to determine if the same report was received previously. If no duplication is identified, the report will be entered into the database. If a duplicate report is later identified through recall or the systematic check for duplicates, the case reported earliest or the one with the most complete data will be maintained as the valid case and updated with any data from the other report not already captured. The duplicate report will be flagged and designated as “Invalid”, with the reason being “duplicate report”.

Evaluable Registry Reports

An evaluable report is a subject with data submitted or confirmed by an HCP that contains at least the minimum criteria for a report and is not lost to follow-up. Prospectively reported evaluable subjects with known outcomes will be included in the primary analysis for the registry report. Evaluable retrospective reports will be summarized separately in the report. Patient-reported data without HCP confirmation will be summarized separately in the report.

Invalid Registry Reports

An invalid registry report is a report for which the minimum data elements are never obtained despite requests for the missing data. If the minimum data are not provided initially, the report will be considered to be pending until all attempts to resolve queries for missing data and requests for follow-up information are complete. If, after all attempts at follow-up are made, the minimum criteria are still not met, the report will be considered invalid due to insufficient information. Invalid reports will not be included in the registry analyses.

Analysis Population

The primary population for analysis will include prospective evaluable subjects exposed to Menveo that are not lost to follow-up (ie, subjects with appropriate outcome information that meet the minimum criteria for evaluation).

Exclusions for Analysis Purposes

Invalid registry reports and pregnancies deemed lost to follow-up will be excluded from the primary analysis. Retrospective reports will not be included, although retrospective cases with MCMs will be reviewed and reported separately for signal detection purposes.

Sequential Pregnancies

The number and outcome of sequential pregnancies will be noted and presented. Sequential pregnancies will be included in the analytic dataset.

Multiple Gestation Pregnancies

The number, type (e.g., twin, triplet), and outcome of multiple gestation pregnancies will be noted and presented. Multiple gestation pregnancies will be included in the analytic dataset.

General Considerations for Data Analyses

This study is observational, and epidemiological methods will be employed for data collection and analyses.

Descriptive analysis will be performed for all prospective, evaluable data. The summary statistics for continuous and categorical variables to be used will be specified in the statistical analysis plan (SAP) but may include means, standard deviations, medians, minimums, maximums, percentiles, n's, and percentages. Adjustment for confounders of potential associations will be made with multivariate regression methods if appropriate and will be described in detail in the SAP.

The registry will identify the number of cases for the primary outcomes of MCM, preterm birth, LBW, and in addition for second trimester SABs; proportions of these outcomes will be calculated with 1-sided 95% confidence intervals from the total number of pregnant women or live births, or in the case of second trimester SABs, the subset of women exposed prior to the 20th week of gestation.

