Maternal Information

- Maternal demographics (age, ethnicity, race)
- LMP
- EDD determined from LMP
- CEDD (e.g., by ultrasound), if available
- Prenatal tests (diagnostic or screening) performed, date of test, and findings including the identification of congenital anomalies

Maternal Obstetrical History

- Number of previous pregnancies
- Outcome of previous pregnancies: live births, stillbirths, SABs, IABs, ectopic pregnancies, molar pregnancies
- History of offspring with congenital anomalies
- Maternal and paternal history of congenital anomalies

Maternal Menveo Exposure (may be provided initially by the pregnant woman at registry enrollment and confirmed by the vaccinating HCP)

- Menveo administration, including dose, timing, and lot number

Other Conditions and Exposures

- Concurrent maternal conditions
- Concomitant medications taken during pregnancy
- Tobacco, alcohol, and illicit drug use during pregnancy

Pregnancy Follow-up

Around the end of the second trimester and in the month of the EDD, the ***Interim Pregnancy Follow-up Form*** and ***Pregnancy Outcome Form*** (respectively) will be requested from the obstetric HCP.

Information Collected at Interim Pregnancy Follow-up and Pregnancy Outcome

Follow-up at End of Second Trimester

Pregnancy Status

- Updates to EDD (ie, CEDD)
- Subsequent prenatal tests (diagnostic or screening) performed and findings including the identification of congenital anomalies
- Pregnancy complications (preterm labor, eclampsia, placental abruption)
- Details of pregnancy outcome if pregnancy is not ongoing as described below

Other Exposures

- Concomitant medications
- Tobacco, alcohol, and illicit drug use during pregnancy

Additional Information Collected at Pregnancy Outcome

Fetal Outcome

- Pregnancy outcome (live birth, stillbirth, SAB, IAB, ectopic pregnancy, molar pregnancy)
- Date of outcome of pregnancy
- Gestational age at outcome
- Fetal/infant characteristics: sex, birth weight
 - MCM(s) and assessment of potential contributing factors
 - For a fetal loss (SAB, stillbirth), factors that may have had an impact on the fetal loss and attribution

Targeted Follow-up Process

If there is an MCM or other event of interest noted, in order to properly characterize the event, additional information may be requested from the reporting HCP on the ***Targeted Follow-up Form***:

- Details of the MCM/condition
- Etiology
- Outcome attribution
- Specific questions requested by NVD and/or the MCM evaluator

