9.7.3 Statistical Methods

Overall and stratum-specific point estimates and 1-sided 95% confidence intervals will be calculated using the exact binomial distribution for prevalence rates of MCMs, preterm birth, and LBW among pregnant women exposed to Menveo and their live births. Most structural defects have their origins in the first trimester of pregnancy, the period of organogenesis. In addition to overall prevalence of MCM, the analysis of MCMs will be stratified by trimester of exposure to Menveo. The prevalence rate of combined MCMs reported to the registry will be calculated as a proportion with the number of MCMs as the numerator and the number of live births as the denominator, among women with first trimester exposure. Pregnancy losses with reported MCMs occurring at or after 20 weeks' gestation will be included in the numerator of the estimate of risk for MCMs to increase sensitivity and to allow comparison of outcomes with the CDC MACDP, which calculates rates by this convention. A secondary analysis will be conducted including pregnancy losses with reported MCMs occurring at less than 20 weeks' gestation in the calculation of risk. The prevalence rate of combined MCMs in exposed cases will be compared with that of the CDC MACDP ([Correa, 2007](#)).

Only cases meeting the CDC MACDP criteria for a defect or with 2 or more conditional defects will be included in the primary analysis. Single minor defects do not constitute a MCM according to the CDC MACDP classification; therefore, they will be listed in the report, but not included in the primary analysis.

The prevalence rate of preterm births and LBW will be calculated as proportions, with the number of live births as the denominator. These prevalence rates in exposed cases will be compared with those of the CDC NVSS ([Martin, 2012](#)). Because MCMs are often associated with preterm birth and LBW, infants with MCMs will be excluded from

analyses of these outcomes and will not be counted in the numerator or denominator when prevalence rates are determined.

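### A congenital anomaly reported on the end-of-second-trimester form enters neither the MCM rate nor any listing the protocol defines if the pregnancy outcome is then not obtained

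*Protocol*

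**What the plan says.** **Data collected before delivery.** Protocol 9.4, under follow-up at the end of the second trimester, asks the obstetric provider for "Subsequent prenatal tests (diagnostic or screening) performed and findings including the identification of congenital anomalies". An anomaly can therefore be in the database well before delivery.

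**Loss to follow-up.** Under 9.7, a prospective pregnancy whose outcome information "is never obtained or is unavailable, the pregnancy will be considered lost to follow-up". The consequence is stated next: "Subjects lost prior to pregnancy outcome will be tallied in the registry reports but not included in the statistical analyses". The exclusions paragraph of 9.7 repeats it: "Invalid registry reports and pregnancies deemed lost to follow-up will be excluded from the primary analysis". The definition of an evaluable report, also in 9.7, again requires that the subject is not lost.

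**Excluded malformations that are kept in view.** The same section makes one exception, for retrospective reports: "retrospective cases with MCMs will be reviewed and reported separately for signal detection purposes".

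**Listings.** The annual updates in 12.2 give line listings that show congenital anomalies for pregnancies whose outcome is known. Lost pregnancies appear there as a number.

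**The rate.** Under 9.7.3 the MCM rate is MCMs over live births, and "Pregnancy losses with reported MCMs occurring at or after 20 weeks' gestation will be included in the numerator".

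**The concern.** None of the loss rules in 9.7 asks whether an anomaly has already been reported. A prospective case with such a report is not retrospective, so the retrospective listing does not take it. Its outcome is unknown, so the 12.2 line listings do not take it either. It is also outside the analysis population. What remains is a count among the lost and a contribution to the baseline summary of the lost group in 9.7.2, neither of which shows the anomaly.

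The protocol regards prospective reports as the less biased source, yet here a prospective malformation gets less visibility in the registry's output than a retrospective one. The registry describes its purpose as detecting safety signals, MCM is a primary outcome, and very few cases are expected. Section 9.5 also expects completion of follow-up among pregnant adolescents to be very low, so the situation is not far-fetched. At stake is whether the reported rate and the signal listings reflect every anomaly the registry has been told about.

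**Working it through.** **Inputs**
- Live births: n = 58 (9.5).
- Background MCM rate: p0 = 0.0254 (9.5).
- Test: exact one-sample binomial, 1-sided 5% (9.6.2).
- Stated power: 80% at a 4.46-fold increase (9.5).

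**Formulas**
- 1-sided p for x cases: P(X ≥ x | n, p0) = Σ from k = x to n of C(n,k) · p0^k · (1 − p0)^(n−k).
- Exact 1-sided 95% lower limit: the 5th percentile of Beta(x, n − x + 1).

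**Step 1: reproduce the protocol's figure.** Expected cases at background are 58 × 0.0254 = 1.47. The smallest count with p ≤ 0.05 is 5, with attained level 0.0159. At p1 = 4.46 × 0.0254 = 0.1133 (58 × 0.1133 = 6.57 expected cases), P(X ≥ 5) = 0.801. The stated 80% reproduces, so the sample-size figure is not in question.

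**Step 2: effect of one omitted case.**

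| Cases / denominator | Rate | 1-sided p against 2.54% | Lower 95% limit |
|---|---|---|---|
| 4/58 | 6.90% | 0.060 | 2.39% (below 2.54%) |
| 5/58 | 8.62% | 0.016 | 3.46% (above 2.54%) |
| 5/59 | 8.47% | 0.017 | 3.40% (above 2.54%) |

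The 5/58 row fits an omitted case that ended as a loss at or after 20 weeks, which 9.7.3 adds to the numerator only. The 5/59 row fits one that ended as a live birth. The reading against the background rate is the same either way.

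**Step 3: trace one case through the rules.** Take a prospective enrollee with an anomaly on the interim form, still pregnant at about 24 weeks, with no outcome form returned.
- 9.7 Loss to Follow-Up: lost, so out of the analyses.
- 9.7 Retrospective Registry Reports and Exclusions: the listing exception does not apply, because the report is prospective.
- 12.2 line listings: do not apply, because the outcome is unknown.
- 9.4.2 and 9.4.4: the anomaly is reviewed and may be classified, but no rule carries the result from there into the rate or a listing.

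Had the outcome been obtained, the pregnancy would have ended in a live birth or in a loss at or after 20 weeks. Either would enter the primary numerator if the finding was classified as an MCM.

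**The case against.** **The case is not hidden from safety review.** This stands. The teratologist/geneticist reviews every reported anomaly (9.4.2), the advisory committee reviews reported MCMs before each registry report (9.4.4), targeted follow-up can be requested (9.4), and MCM is a solicited serious adverse event that goes to the sponsor's safety department (11.0). A reader might infer that a malformation disappears altogether, and the protocol does not support that. The gap is confined to the rate and the defined listings. No sentence forbids listing such a case, and a statistical analysis plan could add it. But the exclusion itself is fixed in the protocol, as is the restriction of the listing exception to retrospective reports.

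**The finding may not be a confirmed malformation.** This also stands. The interim form records screening or diagnostic results, and Table 9.4-1 collects the MCM description at pregnancy outcome. A prenatal finding does not qualify until it is classified.

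**The enrolment rule and the loss rule conflict.** A reader might infer this, because a report counts as prospective only if made "prior to knowledge or perceived knowledge of the pregnancy outcome (e.g., structural defect or genetic abnormality noted on a prenatal test", whereas the same kind of finding after enrolment does not count as an outcome. The two rules serve different ends. The first prevents selection into the registry on a suspected result, and the second asks whether the endpoint was ascertained. This is an asymmetry in handling, not a contradiction.

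**Loss is informative and biases the rate downward.** That is plausible if care moves elsewhere after an anomaly is found, but nothing in the protocol shows it. Outcome data may also come from the pediatrician, and 9.7.4 says the impact of losses cannot be assessed with certainty.

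**Power is seriously eroded.** If 5%, 10%, 20% or 30% of true MCM cases were lost this way, P(X ≥ 5) at a 4.46-fold increase would fall from 80.1% to 76.2%, 71.7%, 61.3% or 49.1%. Those shares are assumptions, and the protocol gives no basis for any of them. Section 9.5 expects about 15 direct enrollees and 60 externally identified exposures a year. If the external sources are networks that report every exposure with its outcome, direct enrollees are 15/75 = 20% of intake, and a 30% share could not arise from them unless they carried more than their share of MCMs. If the 60 is a 3-year total, they are 45/105 = 43%, and a 30% share would need about 0.30/0.43 = 70% of their MCMs to be lost. The range shows sensitivity and is not an estimate.

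**Conclusion.** The point holds in a limited form. As written, a prospective pregnancy with a reported anomaly and no pregnancy outcome is left out of the MCM rate and out of every listing the protocol defines, while an excluded retrospective MCM is reviewed and listed. The primary rate need not change, since a case of unknown outcome has no defined place in a live-birth-based proportion.

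The expected number of such cases is unknown and may be zero. The size is best stated per case: at 4 counted MCMs, one omitted case decides whether the lower limit clears the background rate. This assumes 58 live births, the 2.54% comparator, classification of the finding as an MCM, and use of the lower 1-sided limit, which is the side that matches the power calculation. The protocol calls itself descriptive and sets no formal signal rule. The count of 5 is therefore the threshold implied by its own power calculation, not a declared decision rule. The change is worth making, but its absence does not undermine the primary analysis.

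**What to change.** Add to 9.7, Loss to Follow-Up:

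1. A prospective pregnancy with an anomaly recorded at any contact before loss is classified by the teratologist/geneticist and the advisory committee, and is listed individually in registry reports beside the retrospective MCMs.
2. A pre-specified sensitivity analysis of MCM prevalence adds the lost cases that are classified as MCM and were known to be ongoing at or after 20 weeks. They go into the numerator, and only those same cases go into the denominator (for example 5/59).

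Other lost pregnancies should not be added to the denominator. Their birth examination is unknown, so counting them as free of MCM could bias the rate low. It would also depart from the live-birth convention in 9.7.3 and meet the classification bias that 9.7.4 gives as its reason for excluding losses without a detected MCM.

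**Cost:** a short protocol paragraph, one listing and one sensitivity analysis, all on data already collected. **Downside:** some prenatal findings will be unconfirmed, and lost pregnancies without a finding are not added, so the sensitivity rate leans high and should be labeled as an upper-leaning bound.

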9.2 Setting

9.2.1 Study Period

The pregnancy registry will be implemented after approval by applicable regulatory authority and central institutional review board (IRB). The target enrollment goal of the registry is 100 prospectively enrolled pregnant women. The data collection process for each participant will begin at enrollment (during pregnancy), and follow-up will occur at the end of the second trimester (approximately 24 weeks' gestation) and at pregnancy outcome (delivery or early termination).

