9.3.3 Other Variables

Maternal characteristics: Age, ethnicity, race

Prenatal data: Last menstrual period (LMP), estimated date of delivery (EDD), corrected estimated date of delivery (CEDD)

Prenatal tests: Name of test, date of test, result

Obstetrical history: Previous pregnancies, live births, stillbirths, SABs, induced abortions (IABs), births with congenital malformations, family history of congenital malformations

Concomitant medical conditions

Concomitant medications and vaccines

Alcohol, tobacco, and illicit drug use

Pregnancy outcomes

Each pregnancy outcome will be classified in 1 of the following mutually exclusive categories:

- Live birth: an infant born alive
- Stillbirth: a fetal death occurring at 20 weeks' gestation or greater, or if gestational age is unknown, a fetus weighing 500 g or more
- SAB: fetal death or expulsion of products of conception prior to 20 weeks' gestation. Terminology may include missed abortion, incomplete abortion, and inevitable abortion.
- IAB: voluntary interruption of pregnancy, including pregnancy termination that occurs electively, to preserve maternal health, or due to fetal abnormalities

- Ectopic pregnancy: implantation of a conception outside of the uterus
- Molar pregnancy: a conception that results in a gestational trophoblastic tumor

Infant Outcomes: Gestational age, birth weight, sex

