The outcome data will be stratified by the earliest trimester of exposure to Menveo. For this registry, gestational weeks are estimated from the most reliable EDD as reported by the HCP. If a CEDD is provided by the HCP, it will be used instead. The date of conception will be calculated as the most reliable EDD minus 38 weeks. If the EDD is not available or never estimated, the first day of the LMP may be used to estimate gestational age. The second trimester will be considered to begin at week 14, and the third trimester, at week 28. If there is a discrepancy between gestational age calculated from LMP and reported gestational age, the HCP will be asked to verify the data.

If it is feasible, comparisons between the registry and an appropriate internal and/or external comparison group will be examined (see [Section 9.2.3.1](#) for a description of potential comparators).

Methods to Control for Confounding and Effect Modification

For analyses of associations between pregnancy outcomes and Menveo exposure, confounding and effect modification will be evaluated. A detailed description of these analyses will be available in the SAP. Potential confounders/effect modifiers may include the following:

- Maternal characteristics (e.g., age, ethnicity, race)
- Previous pregnancy outcomes (e.g., MCMs, stillbirth)
- Pregnancy complications (e.g., preterm labor, eclampsia, placental abruption)
- Comorbidities (e.g., diabetes, hypertension)
- Concomitant exposures (e.g., medications, alcohol, tobacco)
- Infant/fetus sex

Subgroup Analyses

Analyses will be stratified by trimester of exposure and other potential subgroups of interest, potentially including gestational age at enrollment and maternal age. Additional details on subgroup analyses will be described in the SAP. Comparisons may be made to external cohorts, if appropriate.

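### The final-outcome loss rule in Protocol 9.7 drops women already known not to have had a second trimester SAB, which pushes that proportion upward by an amount the protocol does not let one fix

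*Protocol*

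**What the plan says.** - **Loss rule.** Protocol 9.7 (Loss to Follow-Up) classes as lost any prospective report for which no information on how the pregnancy ended can be had, and continues: "Subjects lost prior to pregnancy outcome will be tallied in the registry reports but not included in the statistical analyses". Section 9.7.4 adds that pregnancies past their due date with no outcome after four attempts are lost. Evaluable reports and the primary analysis population, also in 9.7, both exclude lost pregnancies.
- **The proportion.** Under General Considerations, 9.7 plans proportions with 1-sided 95% confidence intervals for the three primary outcomes and for second trimester SAB. The denominator is, "in the case of second trimester SABs, the subset of women exposed prior to the 20th week of gestation". The descriptive analysis is restricted to prospective, evaluable data.
- **The event window.** Section 9.3.3 defines the event: "SAB: fetal death or expulsion of products of conception prior to 20 weeks' gestation". Section 9.7.3 gives the lower end: "The second trimester will be considered to begin at week 14, and the third trimester, at week 28".
- **The contacts.** Section 9.2.1: "follow-up will occur at the end of the second trimester (approximately 24 weeks' gestation) and at pregnancy outcome (delivery or early termination"). Table 9.4-1 lists pregnancy status as an item of the interim contact, and section 9.4 adds to that form: "Details of pregnancy outcome if pregnancy is not ongoing as described below".

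**The concern.** The risk window for second trimester SAB closes at 20 weeks, about four weeks before the interim contact. A woman reported as ongoing at that contact has her status for this outcome fully observed. Nothing that happens later, including failure to return the delivery form, can change it. The loss rule looks only at the final pregnancy outcome, so it discards her.

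A woman with an SAB is not exposed to this late loss. If the interim form reports the SAB, her pregnancy outcome is in hand. If that form is missed, the outcome contact can still supply it. Being kept in the analysis therefore depends on whether the event occurred.

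The registry exists to detect safety signals, and section 9.5 expects completion of follow-up among pregnant adolescents to be very low. An estimate raised by avoidable exclusions could be read as part of a signal.

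**Working it through.** The protocol states no expected second trimester SAB proportion, so there is no figure of its own to reproduce.

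**Inputs**
- Event window: week 14 to before week 20 (9.7.3, 9.3.3).
- Interim contact: about 24 weeks (9.2.1).
- Planned enrolment: 100 (9.2.1).
- q, the share of the denominator still pregnant at the interim contact: not stated. Section 9.5 expects about 58% live births, which serves as a low bound. The high value is 0.98, where every non-case is still pregnant and the true risk is 2%.
- d, the share of those women whose delivery outcome is never obtained: not stated. Assumed 20%, 40% and 60%.
- p, the true proportion: assumed 2%.

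**Formula.** Start from N women. Cases stay: p·N. Women still pregnant at the interim contact number q·N, of whom d·q·N are dropped. The planned rule therefore gives p·N / (N − d·q·N) = p/(1 − q·d). Keeping these women as non-cases gives p. The inflation factor is 1/(1 − q·d).

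| d | q = 0.58 | q = 0.98 |
|---|---|---|
| 20% | 1/(1 − 0.116) = 1.13 | 1/(1 − 0.196) = 1.24 |
| 40% | 1/(1 − 0.232) = 1.30 | 1/(1 − 0.392) = 1.64 |
| 60% | 1/(1 − 0.348) = 1.53 | 1/(1 − 0.588) = 2.43 |

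With p = 2%, the expected estimate is 2.3%, 2.6% and 3.1% at q = 0.58, and 2.5%, 3.3% and 4.9% at q = 0.98.

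**Example with exact binomial limits.** Take 100 women and 2 SABs. The protocol does not say which side its 1-sided 95% interval takes, so both limits are shown.

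| Denominator | Estimate | Lower limit | Upper limit |
|---|---|---|---|
| All 100 kept | 2.00% | 0.36% | 6.16% |
| 58 still pregnant, 20% lost (12): 2/88 | 2.27% | 0.41% | 6.98% |
| 58 still pregnant, 40% lost (23): 2/77 | 2.60% | 0.46% | 7.95% |
| 98 still pregnant, 20% lost (20): 2/80 | 2.50% | 0.45% | 7.66% |
| 98 still pregnant, 40% lost (39): 2/61 | 3.28% | 0.59% | 9.96% |

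**Equal response at both contacts.** The asymmetry does not need cases and non-cases to respond differently. Suppose each contact is answered independently with probability r. An SAB is kept if either is answered, 1 − (1 − r)². A continuing pregnancy is kept only if the outcome contact is answered, r. The ratio is 2 − r: 1.2 at r = 0.8 and 1.4 at r = 0.6.

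**What would cancel it.** At q = 0.98, with no early loss among other women, the share of SABs missed altogether would have to equal d (20% or 40%). With 10% early loss among the others, it would have to reach 1 − 0.9 × 0.8 = 28% or 1 − 0.9 × 0.6 = 46%.

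**The case against.** **The net direction is not shown.** This stands. Section 8.0 explains that late enrolment hides SABs and that early ones may go unrecognised or unreported. Women enrolled after week 20 also sit in the denominator although they can no longer have an SAB. These forces lower the proportion. A reader might infer that the reported figure will be too high overall; the documents support only the direction of this one mechanism.

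**A missed interim form does not remove a non-case.** This also stands. A reader might infer that a non-case needs both forms returned. Sections 9.7 and 9.7.4 require only the final outcome, and section 9.4 re-opens a case if data arrive later.

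**The larger factors may not apply.** Many of these pregnancies are expected to end in induced abortion. Those ended before 24 weeks can be captured at the interim contact and stay in the denominator, which is why q = 0.58 belongs in the range. Section 9.5 also expects about 60 exposures from external sources against about 15 a year from the registry system. Section 9.7 describes provider networks and HMOs as supplying data on every exposed pregnancy, so late loss there may be small. The expectation of very low completion carries no rate, so no value of d can be called the protocol's own.

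**The outcome is secondary in weight.** Agreed. It is an additional descriptive outcome with no stated comparator or power. A reader might also lean on section 7.0, where all 7 SABs in the earlier trials were in MenACWY recipients. But 37 of the 43 pregnant women had received MenACWY. If SABs fell at random among the 43, all 7 would be in recipients with probability C(37,7)/C(43,7) = 0.32. That section does not say these were second trimester losses.

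**Section 9.7.4 already concedes loss bias.** Only in general terms: it says the impact cannot be assessed with certainty and offers a possible comparison of characteristics. Here the woman's status is on file and is discarded, so this component can be removed.

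**Conclusion.** The point holds as a flaw in one denominator. Sections 9.7 and 9.7.4 define loss by the final pregnancy outcome, 9.7 removes lost women from the statistical analyses, and nothing exempts second trimester SAB. Compared with keeping women documented as still pregnant at the interim contact, the rule can only raise the proportion. The factor is 1.13 to 1.53 at q = 0.58 and 1.24 to 2.43 at q = 0.98, for assumed late loss of 20% to 60%. It exceeds 1 for any late loss above zero. The sizes rest on assumed d and on a range for q whose lower end is borrowed from the live-birth share. With about two cases expected per 100 women at an assumed 2% risk, sampling error is large beside this bias. The primary outcomes are not affected by this argument. The change is worth making because the rule is written into the protocol and the correction uses data already planned.

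**What to change.** In Protocol 9.7, make the loss rule outcome-specific. For second trimester SAB:

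- Restrict the denominator to prospective women both exposed and enrolled before week 20, so that everyone counted could still have had the event when she entered.
- Include every such pregnancy with a known outcome at any gestational age. SABs and induced abortions reported before week 20 then stay in.
- Also include every such pregnancy documented as ongoing at 20 weeks or later, counted as a non-event even if the delivery outcome is never obtained.
- Treat as lost only pregnancies with neither.

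The live-birth-based outcomes keep the existing rule.

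The cost is a short addition to 9.7, carried into the SAP. No new data are needed, because the interim form already collects pregnancy status. The downside is that the SAB denominator will differ from the set used for the other outcomes, so reports should show both counts. The change does not recover SABs that are never reported, and that limitation should still be stated.
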